a.7. Exogenous Melatonin and Delirium Prevention: findings are mixed. Two trials in postoperative patients used superphysiologic doses: the first using 7.5 mg melatonin orally the night prior to, and a second dose 90 minutes before surgery. Active treatment was compared to patients receiving two other agents or no drug at all. A placebo was not used. The new occurrence of delirium on days 0-3 in the groups with no drug treatment vs. melatonin was 33% vs. 9%, respectively. ⁵⁷ The second was a recently published placebo-controlled RCT, testing oral doses of 3 mg of melatonin, administered for 5 consecutive nights in 378 older patients (mean age 84 years) undergoing hip fracture repair. This trial demonstrated neither delirium preventive effect (55/186 or 30% among melatonin group vs. 49/192 or 26% in the placebo) nor any functional differences at 3 months. ⁵⁸ Secondary analysis revealed that patients treated with melatonin, had fewer episodes of delirium lasting longer than 2 days, compared to placebo. ⁵⁸ Another placebo-controlled RCT was conducted in a medically ill patient population aged 65 and older using a physiologic dose of 0.5 mg of melatonin at bedtime for up to 14 days during a medical hospitalization. ⁵⁹ The delirium prevalence in placebo vs. melatonin (31% vs.12% respectively; p<0.02) resulted in an absolute risk reduction of 15.6% (NNT = 6.4).

a.8. Advantages of Ramelteon – include quality control and longer drug effect. Unlike melatonin, which is considered a dietary supplement, ramelteon is an FDA-regulated pharmaceutical. Inadequate comparability of biologic availability of melatonin, between different manufacturers and even between batches from the same company, has been cited as a major barrier to studying the effects of exogenous melatonin in clinical trials. ³⁶ As a regulated drug, ramelteon,

has distinct advantages with respect to quality control and comparable melatonergic activity. Furthermore a biologically active metabolite M-II contributes to a longer total drug effect of 5 hours compared to 1- 2 hours for melatonin.^{39,60}

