a.9.Ramelteon and Delirium Prevention: Promising in medically ill patients. A trial employing ramelteon in a delirium prevention study of 67 medically ill patients, > 65 years of age demonstrated a significant reduction in delirium in ramelteon-treated vs. placebo (3% vs. 32% respectively; $p = 0.003$) reflecting a relative risk (RR) of 0.09 (95% CI 0.01-0.69).²⁴ Of 1,126 patients screened, 101 met inclusion criteria. Exclusions included a length of hospital stay or life expectancy < 48 hours, diagnosis of 1) liver failure, 2) Dementia with Lewy Bodies, 3) alcohol dependency, 4) psychotic disorder, 5) bipolar disorder, or 6) prior use of fluvoxamine. Outcome measures were DSM –IV⁶¹ based delirium diagnosis and DRS-98R⁶² as assessed by study psychiatrists. The intervention and control groups were balanced regarding important confounders: patients were comparable in baseline demographics, levels of baseline dementia and severity of illness. No one stopped the ramelteon due to adverse outcomes. The most significant risk of bias was due to a non-identical appearing placebo, potentially leading to unmasking of treatment assignment.

a.10. Summary of Significance: Sleep disruption is a central feature of delirium, and preliminary data suggests that melatonin deficiency is associated with postoperative delirium in older adults. The use of ramelteon as a melatonin agonist perioperatively could prevent delirium by a number of mechanisms including enhancing circadian rhythm and promoting sleep, direct antioxidant and anti-inflammatory activity and central dopamine blockade. While results of melatonin RCTs have been quite mixed, ramelteon offers pharmacokinetic and pharmacodynamic advantages over melatonin that may enhance potential benefits. Successful prevention of postoperative delirium will result in improvements in the lives of older patients undergoing surgery and significant cost-savings to the healthcare system.

b. Innovation:

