Randomization: A statistician ([name]) will be responsible for design, implementation, and maintenance of randomization procedures that assign participants to active pharmaceutical or placebo. Since preoperative cognitive impairment is consistently and strongly associated with the development of postoperative delirium, our randomization process will stratify by preoperative MMSE exam score to ensure balanced allocation (MMSE score 24/30 - 30/30 and 15/30 - 23/30). Under supervision of the statistician, research pharmacy staff who have no contact with the patient or clinical staff will randomize participants using a computer program, utilizing dynamic allocation probabilities to balance the two groups on the dichotomous MMSE variable.

Masking Procedures: The research pharmacy staff will prepare the active treatment (ramelteon 8 mg) and placebo using identical gel caps containing 100 mg riboflavin for doses to be self-administered outside of the hospital. No riboflavin will be added to study doses to be administered by hospital nursing staff. Once randomized, the assigned agent will be labeled with the patient's name and medical record number with the administration instructions consistent with hospital policy. No markings will indicate identity of the agent. Participants admitted on the day of surgery will receive the assigned study medication (active treatment/placebo) at the study visit prior to surgery. For all inpatient doses clinical nursing staff will administer medication each evening (8-10 pm). Administration will be documented in the clinical electronic medication record and adherence closely monitored by research staff.

Concomitant Medications: All medications except those enumerated in exclusions will be allowed.⁶⁰

Choice of Clinical Site and Feasibility of Recruitment: A total of 198 infection-free inpatients ≥ 65 years of age, underwent total hip or knee arthroplasty or revision under general anesthesia between 01/01/14-12/31/14 at JHBMC. The median (IQR) ASA physical status score and median surgical duration (IQR) was 3 (3-3) and 172 (122-216) mins. respectively, reflecting significant comorbidity and lengthy surgical times, consistent with high postoperative delirium risk likely to be at least 30%.⁵⁸

b. Study duration and number of study visits required of research participants.

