Choice of Sample Size; Power Considerations– Why 80 adherent participants? The power to detect a difference in the development of postoperative delirium of an the previously reported effect-size²⁴(30% placebo-treated vs. 3% ramelteon-treated) is greater than 0.90, using the current design of 40 participants in each treatment arm and assuming 30% of the placebo-treated group will develop delirium on POD 1 or 2. This design can detect an 80% reduction in delirium (30% placebo-treated vs. 6% ramelteon-treated) with a power of 0.84. A conservative estimate for power for the continuous outcome (DSRS-98R) measuring delirium severity can be derived by conceptualizing the proposed longitudinal analysis as an independent samples t-test. With alpha of 0.05 and a sample size of 80, and with means in the ramelteon and placebo groups of 5.75 and 11.34, respectively (as reported in Hatta, et al), and SDs of 4.16 and 10.96, we would have 84% power to detect that difference. Power for the planned analysis, which includes 3 post-surgery measurements per participant, and controls for baseline measurement and additional covariates would likely be greater.

Data Analysis-Specific Aim 1:

Analysis 1: Odds of postoperative delirium upon immediate recovery will be modeled via logistic regression with treatment assignment as the covariate of interest, and controlling for baseline MMSE, surgical duration and sleep disorders in all randomized participants in a strict intent to treat model and also in a second analysis among the 80 first-dose adherent participants.⁹¹ Odds of delirium on POD's 1 and 2 will be modeled via a Markov logistic regression model⁹² as a function of treatment assignment, baseline MMSE, and mental status on

the previous day, where two transitions are possible: from normal mental status to delirium and/or coma (abnormal mental states) and the reverse. Correlation of mental status on consecutive days for the same individual will be modeled using generalized estimating equations (GEE).⁹² We will fit models with interactions between treatment group and variables hypothesized to predict treatment response, including baseline MMSE and sleep to determine if treatment response varies as a function of baseline predictors.

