Analysis 2: The continuous DRS-98R severity measure of delirium will be modeled via longitudinal linear regression with correlated observations within participants addressed via the method of GEE with treatment assignment as the covariate of interest and controlling for baseline DRS-98R score, MMSE, surgical duration and sleep disorders.

Data Analysis-Specific Aim 2: Risk of a severe adverse event will be modeled as a function of treatment assignment using logistic regression, as will counts of total adverse events using ordinal logistic regression or Poisson regression as appropriate. Counts of each specific type of AE, as a function of treatment assignment will be scrutinized to determine the power needed to study them in future larger-scale trials.

- d. Early stopping rules. This is a pilot study and will continue until 80 adherent participants are recruited. A Data Safety Monitoring Board will review the data at the end of year one or at recruitment of 40 adherent participants (whichever comes first) to review the unblinded (labelled "A" and "B") data for safety of the intervention. Specifically, for the analyses of rates of delirium in the two groups, we will use a Haybittle-Peto boundary such that the alpha for the interim analysis will be 0.001, and the alpha for the final efficacy analysis will be 0.05.

8. Risks

- a. Medical risks, listing all procedures, their major and minor risks and expected frequency.

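### Does the loosely cited delirium risk of at least 30% undermine the stated power?

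*Combined protocol and SAP*

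**What the plan says.** Section 4a of the combined protocol and SAP, under Choice of Clinical Site and Feasibility of Recruitment, describes 198 hip or knee arthroplasty and revision patients. It gives their ASA scores and surgical durations and concludes that these are "consistent with high postoperative delirium risk likely to be at least 30" percent. The citation is reference 58, the placebo-controlled melatonin trial in hip fracture repair.

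Background a.7 gives that trial's results as "55/186 or 30% among melatonin group vs. 49/192 or 26% in the placebo". Background a.9 describes the earlier ramelteon trial in medically ill patients (reference 24) as showing a "significant reduction in delirium in ramelteon-treated vs. placebo (3% vs. 32% respectively").

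Section 7c states its power for 40 per arm, and the same sentence sets out the placebo rate as an assumption: "assuming 30% of the placebo-treated group will develop delirium on POD 1 or 2". For the effect size of the earlier ramelteon trial the claim is "30% placebo-treated vs. 3% ramelteon-treated) is greater than 0.90". For a smaller effect it says: "This design can detect an 80% reduction in delirium (30% placebo-treated vs. 6% ramelteon-treated) with a power of 0.84". The early-stopping section (7d) adds that "the alpha for the final efficacy analysis will be 0.05". Section 7c gives power for the binary outcome at no other placebo rate and names no test for the two proportions.

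**The concern.** A source with 26% delirium on placebo cannot establish that untreated patients run a risk of at least 30%. The only 30% in that trial is in the arm given melatonin, and both arms together give 104/378 = 27.5%. The trial's patients had hip fractures and a mean age of 84, whereas the site figures concern arthroplasty patients aged 65 or over, so carrying the rate across is a further step.

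If the planning rate in section 7c rested on this citation, the power would be overstated. For an 80% reduction with 40 per arm, power falls below 0.80 once the placebo rate is under about 27% to 28%, and 26% is below that. A reader weighing a negative result against a stated power of 0.84 could then take it as stronger evidence than it is.

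**Working it through.** **Inputs.** From section 7c: 40 per arm, 30% on placebo, 3% or 6% on ramelteon. From section 7d: alpha 0.05, taken as two-sided because sidedness is not stated for the proportions. From Background a.7: 49/192 and 55/186.

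**The cited trial.** 55/186 = 29.6% and 49/192 = 25.5%. The Wilson 95% interval for 49/192 is 19.9% to 32.1%, which contains 30%.

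**Formulas.**
- Unpooled z: power = Φ(|p1 − p2| / √[(p1q1 + p2q2)/40] − 1.96).
- Arcsine: power = Φ(h√20 − 1.96), with h = |2 asin√p1 − 2 asin√p2|.
- Exact: the sum of binomial probabilities over all tables in which the uncorrected chi-square test rejects.

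**The plan's own figures.**
- 30% vs 6%, unpooled: the standard error is √[(0.2100 + 0.0564)/40] = 0.0816, so 0.24/0.0816 = 2.941 and Φ(0.981) = 0.837.
- 30% vs 6%, arcsine: h = 0.664, h√20 = 2.971 and Φ(1.011) = 0.844. Exact: 0.845. Stated: 0.84.
- 30% vs 3%: 0.937 unpooled, 0.952 arcsine, 0.956 exact. Stated: above 0.90.

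Both figures reproduce. A pooled z (0.810) or Fisher's exact test (0.768) would not give 0.84 for 30% vs 6%, so the unnamed method was evidently one of the three above or close to them.

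**Other placebo rates, 40 per arm (unpooled / arcsine / exact).**

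| Placebo rate | 80% reduction | Against 3% |
|---|---|---|
| 26% | 0.763 / 0.779 / 0.781 | 0.871 / 0.898 / 0.903 |
| 30% | 0.837 / 0.844 / 0.845 | 0.937 / 0.952 / 0.956 |
| 33% | 0.881 / 0.883 / 0.884 | 0.967 / 0.975 / 0.977 |

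For 26% vs 5.2%, unpooled: 0.208/0.0777 = 2.676 and Φ(0.716) = 0.763. At the cited trial's pooled 27.5% an 80% reduction has power 0.79 to 0.81. If the 90% relative reduction of 30% to 3% is kept at 26% (26% vs 2.6%), power is 0.89 to 0.92.

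**What else the document says about untreated risk.** Background a.7 gives 33% on days 0 to 3 in the no-drug group of a surgical melatonin trial; the reference list shows that this was hip arthroplasty under spinal anesthesia in the elderly. It also gives 31% on placebo in medical inpatients. Background a.9 gives 32% on placebo in the earlier ramelteon trial. Background a.1 gives up to 60% after major surgery, and section 4a gives 45% in early recovery from general anesthesia, which is a different window from POD 1 and 2. Against these, 30% is a middling planning value.

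**The case for a change.** The strongest case for acting is that the trial is meant to inform a phase 3 decision, so its power statement will be read closely. The one placebo-arm rate the document reports in surgical patients is 26%, and there the power for an 80% reduction is below 0.80. The 33% surgical control received no drug rather than a placebo and had spinal anesthesia, so it is an imperfect counterweight. The trial also excludes patients with MMSE below 15, a group likely to be at higher risk. A corrected sentence and a short table of power by placebo rate would cost almost nothing.

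Much of this stands as fact: the citation is wrong for the claim attached to it, and a range of placebo rates would be good practice. What does not stand is the harm. The reader is told in the power sentence itself that 30% is assumed, and the 0.84 sentence repeats both rates. The faulty citation sits in a paragraph about site and recruitment, is hedged as likely, and argues from ASA scores and operating times as well. Section 7c does not cite it; its effect-size citation is the earlier ramelteon trial, whose control rate was 32%. A table of simple two-proportion power would also only approximate the planned logistic and Markov models.

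**Conclusion.** No change to the plan is called for. This is a citation slip in a feasibility paragraph together with an absent sensitivity range; it is not an error in the sample size. The stated power is right at 30%, is presented as conditional on 30%, and 30% is compatible with the document's own data.

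If the true placebo rate were 26%, power for an 80% reduction would drop by about 6 to 7 points, to 0.76 to 0.78, and power against 3% would be 0.87 to 0.90. About 42 to 44 per arm would bring the former back to 0.80. Section 4f keeps recruiting until 80 participants have documented first-dose adherence and analyses everyone randomized, so the number analysed may exceed 80, although non-adherent participants would dilute the effect. In a proof-of-concept trial that is a fair margin, and no decision on enrolment, analysis or conduct turns on it.

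This rests on a two-sided alpha of 0.05, equal arms of 40, and a simple comparison of two proportions standing in for the planned models.

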Choice of dosing times: include three consecutive evenings: 1) prior to surgery, 2) the night of surgery or POD 0 and 3) POD 1. The preoperative administration of ramelteon is designed to correct melatonergic deficiencies observed immediately following surgery and to enhance circadian rhythm and sleep effects.⁵⁴ Participants who are admitted to hospital the night before surgery will have study assigned medication administered by clinical staff, similar to the procedure for POD 0 and POD 1 doses. Participants undergoing elective surgery are given the first dose of medication at their preoperative study visit with instructions to take it the night before surgery. Study personnel will contact to remind the participant. Lack of adherence to self-administration of medication has been described as a barrier in the literature.⁷² Serving as a biologic tracer, 100 mg of riboflavin (Vitamin B₂) will be added to both the active agent and placebo of doses to be self-administered

outside of the hospital. Since riboflavin fluoresces under UV light, a urine sample obtained in the OR at the time of catheterization, will be sent for quantitative fluoroscopy using a cutoff of > 900 ng/ml as evidence of adherence. Replacement recruitment will be completed for any participants with urine samples negative for riboflavin.

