The patient will be asked to take the study medication (either ramelteon or placebo - both containing riboflavin) the night before surgery. For many patients this will occur at home prior to admission and research personnel will place telephone calls to ensure adherence by the patient. While in the hospital the patient will have a urine sample collected and sent on the day of surgery to test for riboflavin, will be visited by study staff to do a delirium assessment in the PACU upon recovery from anesthesia, and on two subsequent postoperative days. Two doses of the study drug will be prepared by the research pharmacy and administered by the patient's nurse. Blood will be drawn for biomarkers on POD1 and POD2. For the biomarker collection on POD1 and POD2, 5 ml (1 teaspoon) of blood will be collected during routine AM blood draw, and therefore will not involve an additional needle stick. If the participant is discharged from the hospital early (prior to POD2), the biomarker collection for that day will not be completed. For participants who are discharged from the hospital on postoperative day 0 or day 1, the remaining doses of study medication will be packaged by the pharmacy and given to the participant to take at place of discharge with instructions to take the medication at hour of sleep. Study staff will call the participant and complete the study questionnaires each day by telephone should the patient be discharged prior to postoperative day 2.

c. Blinding, including justification for blinding or not blinding the trial, if applicable.

Blinding of study staff, clinical staff and the patient is critical for the design and the study aims – which seek to test whether ramelteon might prevent the development of postoperative delirium.

d. Justification of why participants will not receive routine care or will have current therapy stopped.

Date: 12/18/17

Principal Investigator: [name]

Application Number: IRB00097232

Participants will receive routine surgical and postoperative care. The study seeks to add exposure to ramelteon or placebo to test whether this intervention might decrease delirium - a common complication that occurs in the postoperative setting in older adults. No current therapy will be stopped.

e. Justification for inclusion of a placebo or non-treatment group.

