The inclusion of a placebo treatment is critical in helping advance our understanding of the effects (both positive and negative) of ramelteon exposure. Placebo comparison is the only way that we can understand what is likely due to ramelteon and what is not.

f. Definition of treatment failure or participant removal criteria.

All consented participants will be retained in the study. Participants with no evidence of riboflavin in the urine sample as tested by fluorescence prior to surgery (i.e. evidence of non-adherence to the first dose of study agent) will continue in the study, receiving second and third doses of study agent, and undergoing delirium outcome measures at all time points; however recruitment will continue until 80 participants with documented adherence to the first doses of study agent is attained. Primary analysis will be intent to treat with all randomized subjects included in the analysis; secondary analysis will include only patients with documented adherence all 3 doses of study medication (a per protocol analysis).

Participants who have their surgery canceled after they have been randomized and who are likely to have surgery in the future will be considered "suspended" from the study. These participants will continue in their assigned condition. A new baseline will be completed prior to their new surgery date to establish that they continue to meet inclusion criteria. The team will proceed with the protocol pre- and postoperatively as assigned during the original randomization. If the participant takes any of the study medication prior to the original surgery, a minimum of 7 days between initial study dosing and the re-initiation of the protocol is required to ensure sufficient time to wash out. If the rescheduled surgery occurs less than 7 days after original dosing, the participant will be excluded from the study.

g. Description of what happens to participants receiving therapy when study ends or if a participant's participation in the study ends prematurely.

Patients will be thanked for their help with the study and will be advised to call the PI with any questions.

5. Inclusion/Exclusion Criteria

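### The all-3-doses per-protocol set depends on doses due after the PACU and POD 1 outcomes, differs from the first-dose set in the statistical plan, and has no stated record for doses taken after discharge

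*Combined protocol and SAP*

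**What the plan says.** Section 4.f (Definition of treatment failure or participant removal criteria) sets the primary population: "Primary analysis will be intent to treat with all randomized subjects included in the analysis". It then adds that "secondary analysis will include only patients with documented adherence all 3 doses of study medication (a per protocol analysis", without saying which outcomes this covers.

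Section 7.c (Data Analysis, Specific Aim 1, Analysis 1) fits the PACU model in all randomized participants "and also in a second analysis among the 80 first-dose adherent participants". It names no adherent set for the POD 1 and 2 delirium model. Nor does Analysis 2 for DRS-98R severity.

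On timing, Section 4.a (Choice of dosing times) says the doses "include three consecutive evenings: 1) prior to surgery, 2) the night of surgery or POD 0 and 3) POD 1". Masking Procedures, in the same section, puts inpatient doses between 8 and 10 pm.

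On documentation, Section 4.a relies on "a urine sample obtained in the OR at the time of catheterization" to test for the riboflavin tracer. Inpatient doses go into the electronic medication record, and the assessment table in Section 7.a lists chart review as the source for study-agent data. For participants discharged on POD 0 or POD 1, Section 4.b says "the remaining doses of study medication will be packaged by the pharmacy and given to the participant to take at place of discharge". Staff then telephone daily to complete the study questionnaires.

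**The concern.** An adherent analysis is useful only if adherence is judged on doses that could have influenced the outcome. A rule requiring all three doses also uses doses due after the outcome has been rated. A participant who is delirious in the PACU and misses the POD 0 dose would leave the set because of something that happened after the PACU rating, and perhaps because of it. Early discharge may work the other way: participants who recover quickly take later doses at home, where no record is specified, and may fall out of the set although adherent.

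The disagreement between Sections 4.f and 7.c adds a second problem. With two adherent sets on paper and no statement of which applies to which outcome, the choice can be made after results are seen. Rigorous adherence is presented as a strength of this trial (Section 3.b.3), and its results are meant to inform a phase 3 decision, so the adherent analysis is likely to be read closely.

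**Working it through.** **Step 1: doses against outcomes.** Dose times are from Section 4.a and outcome times from Choice of study population and outcome measurement time points. The clock time of the POD 1 assessment is not stated; daytime is assumed.

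| Outcome | Doses due before | Doses due after |
|---|---|---|
| PACU | 1 | 2, 3 |
| POD 1 | 1, 2 | 3 |
| POD 2 | 1, 2, 3 | none |

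The 3-dose rule matches only the POD 2 row. Using the first-dose set for PACU incidence does not settle the matter for severity. Section 7.c says the severity analysis uses three post-surgery measurements per participant, and Section 4.f gives the only adherent rule that could apply to it.

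**Step 2: doses against records.**

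| Dose | Record specified |
|---|---|
| 1, taken at home | urine tracer in the OR |
| 1, if admitted the night before | medication record |
| 2 and 3, in hospital | medication record |
| 2 and 3 after POD 0 discharge; 3 after POD 1 discharge | none stated |

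No later urine sample is planned. The documents do not say that the daily call asks about intake or that a reported dose counts as documented.

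**Step 3: the plan's own figure.** The stated power of 0.84 for 30% vs 6% with 40 per arm reproduces with the unpooled normal formula, two-sided alpha 0.05 assumed: SE = √(0.30×0.70/40 + 0.06×0.94/40) = 0.0816; 0.24/0.0816 − 1.96 = 0.98; power 0.84. It is not in dispute. These rates serve as the base for Step 4.

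**Step 4: what retention linked to delirium would do.** The documents give no missed-dose or early-discharge rate, so all retention values are assumptions. Let a be the share of delirious and b the share of non-delirious participants who enter the set. The rate seen is p·a / (p·a + (1−p)·b).

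Same a and b in both arms, true rates 30% and 6%:

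| a | b | Placebo | Ramelteon | Difference (points) | Kept of 80 | Odds ratio |
|---|---|---|---|---|---|---|
| 1 | 1 | 30.0% | 6.0% | 24.0 | 80 | 0.149 |
| 0.5 | 0.9 | 19.2% | 3.4% | 15.8 | 66 | 0.149 |
| 0.7 | 0.9 | 25.0% | 4.7% | 20.3 | 69 | 0.149 |
| 0.9 | 0.5 | 43.5% | 10.3% | 33.2 | 46 | 0.149 |

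Example, fourth row, placebo: 0.30×0.9 / (0.30×0.9 + 0.70×0.5) = 0.27/0.62 = 0.435. The unadjusted odds ratio does not move, because the factor a/b cancels between arms.

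Different retention by arm, no true effect: the odds ratio seen is (a/b on ramelteon) / (a/b on placebo).

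- Delirious kept 70% on ramelteon and 90% on placebo, non-delirious 90% in both: 0.7/0.9 = 0.78.
- Delirious kept 50% on ramelteon and 90% on placebo, non-delirious 90% in both: 0.5/0.9 = 0.56.
- Delirious kept 90% in both, non-delirious 50% on ramelteon and 70% on placebo: (0.9/0.5)/(0.9/0.7) = 1.40.

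The error can favour either arm.

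**The case against.** The primary analysis is intent to treat and keeps everyone randomized, so at most a secondary analysis in a proof-of-concept trial is touched. Any per-protocol analysis conditions on events after randomization. For PACU incidence, Section 7.c already uses first-dose adherence, which is the set one would ask for. The POD 1 and 2 model adjusts for the previous day's mental status, which may partly absorb dose loss driven by earlier delirium. Eligibility requires a planned inpatient stay, and the documents mention only a trend to early discharge. The package-insert figures in Section 8.a show small differences between ramelteon and placebo (somnolence 3% vs 2%, discontinuation for adverse events 6% vs 2%), well short of the 20- to 40-point gaps in retention used in Step 4.

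Most of this stands and limits the point. It also rules out three stronger readings that a reader might draw:

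- That post-discharge doses cannot be documented. The daily call could record intake; the plan simply does not say that it does.
- That the set is selected on delirium itself. It is selected on adherence and possibly discharge. A link with delirium is plausible but not shown, and the two mechanisms pull in opposite directions.
- That the per-protocol result would favour ramelteon. Nothing in the documents supports a direction.

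The objection does not remove the conflict between Sections 4.f and 7.c, the mismatch in timing, or the silence on take-home doses.

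**Conclusion.** The point holds in limited form. As written, the 3-dose set conditions on doses due after the PACU outcome and, assuming a daytime rating, after the POD 1 outcome. It differs from the adherent set in Section 7.c, and it has no stated documentation for doses taken after early discharge. The consequence is confined to the secondary adherent analysis.

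Its size cannot be derived from the documents. With assumed retention of 50% to 90% applied equally in both arms, the apparent risk difference ranges from 16 to 33 points against a true 24, with the odds ratio unchanged. Since the plan models odds, the planned effect measure is at risk only if retention linked to delirium differs between arms. In the assumed examples, a null effect then shows an odds ratio between 0.56 and 1.40. These figures show what is possible; they are not forecasts. The plan should be changed because the correction is cheap and removes a choice that could otherwise be made after seeing results.

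**What to change.** Amend Sections 4.f and 7.c so that they agree, before unblinding:

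1. Make the first-dose-adherent analysis the main adherent analysis for every outcome: PACU, POD 1 and 2 delirium, and DRS-98R severity. First-dose adherence is also observed after randomization, but it is settled before any postoperative outcome is rated.
2. In any later-dose analysis, count only doses due before the outcome (PACU: dose 1; POD 1: doses 1 and 2; POD 2: doses 1 to 3). Label it supportive, because dose 2 falls after the PACU rating and dose 3 after the POD 1 rating, so it still conditions on post-randomization events.
3. Define documented adherence for each dose, and count intake reported in the daily telephone call as documentation of take-home doses.

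The cost is protocol wording plus one intake question in a call already planned. There are two drawbacks. Self-reported intake is weaker evidence than a tracer or medication record. The sets would also differ by day within the POD 1 and 2 model, so a participant could contribute to one day and not the other; the plan should say how that is handled.
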